Neurofilament light chain, inflammatory markers, calcitonin gene-related peptide, and kynurenone metabolites in patients with severe post- concussive symptoms

STATISTICAL ANALYSIS PLAN

NCT ID NOT YET ASSIGNED, FEBRUARY 28TH, 2023

[name]

Statistical analyses plan

At baseline (before randomization):

1) Concentration differences between groups

Concentration differences of biomarkers between patients and controls were assessed using two-way ANOVAs with gender and group (patient/control) as factors. This approach was used since gender differences are known for some biomarkers.

Before the test was conducted, normality was assessed using QQ-plots after log transformation and Barlett's test was used to test for equal variances. Interaction between group and gender was tested, and removed from the model if it was non-significant.

If statistical significantly differences were found, a post-hoc-analyses using Fisher's protected least-significant difference were conducted.

If Barlett's test showed unequal variances, a mixed model allowing for variance heterogeneity was used.

If data was not normally distributed, Kruskal Wallis test was used.

Neurofilament light chain was included as the primary outcome in this study since it is highly specific for brain tissue, and multiple studies have shown concentration differences between healthy controls and concussion patients.

Calcitonin-gene related peptide was included as a primary outcome as well (separate study) since it is related to headache.

2) Correlation between symptom score and biomarkers

The correlation between biomarkers and symptom score measured by the Rivermead Post Concussion Symptoms Questionnaire was tested by Spearman's Rank Correlation or Pearson correlation coefficient (depending on whether the data were normally distributed or not).

Neurofilament light chain and TNF-alfa were included as the primary outcomes since multiple previous studies have found an association.

At follow-up (after randomization):

1) To test whether the concentrations changed at follow-up, a paired t-test was used on all concussion patients regardless of the intervention (n=54). Before conducting the test, normality of the differences was assessed using QQ-plots, and variances were assessed using Bland Altman plots. If the data were not normally distributed or had unequal variance, a Wilcoxon signed-rank test was used.

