2) To test whether the non-pharmacological intervention had an effect on the biomarkers, a two-way ANOVA on concentration differences (baseline – follow-up) was performed with gender and intervention arm as the two factors. This was included as a secondary outcome in the study, since we

did not believe that the biomarker change would be sensitive enough to detect changes in RPQ/psychology due to the non-pharmacological intervention.

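### The only randomised comparison uses change scores without baseline concentration as a covariate: valid, but less precise than a baseline-adjusted model unless the baseline slope is close to 1

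*SAP*

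**What the plan says.** Item 2 under At follow-up (after randomization) has this purpose: "To test whether the non-pharmacological intervention had an effect on the biomarkers". The method is "a two-way ANOVA on concentration differences (baseline – follow-up) was performed with gender and intervention arm as the two factors". Its status follows: "This was included as a secondary outcome in the study". The SAP adds that the authors doubted the biomarkers were sensitive enough to pick up an effect of the intervention.

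No other analysis in the SAP compares randomised arms:

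- The baseline group comparison uses "two-way ANOVAs with gender and group (patient/control) as factors" and precedes randomisation.
- The correlation of biomarkers with symptom score is also a baseline analysis.
- The paired t-test at follow-up (item 1) pools all 54 patients whatever their arm.

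For the baseline group comparison, "normality was assessed using QQ-plots after log transformation". Item 2 at follow-up does not say whether its differences are on the raw or the log scale.

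**The concern.** Subtracting follow-up from baseline assumes that a patient who starts one unit higher ends one unit higher. For a marker with measurement error and within-person variation, the slope of follow-up on baseline is often not 1. The change then correlates with the baseline value, and any chance difference in baseline between the arms leaks into the estimated arm effect. Randomisation makes that leak zero on average, so it appears as extra variance and not as bias.

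What is at stake is the width of the interval for the one randomised comparison, in a sample of 54. The baseline value exists for every patient who has a change score, so adjusting for it loses no patients. The SAP covers several kinds of biomarker, and a single fixed slope of 1 may not suit them all.

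**Working it through.** **Inputs.** From the SAP: 54 patients (At follow-up, item 1) and a model with arm and gender (item 2). With the intercept, this leaves 54 − 3 = 51 residual degrees of freedom. The SAP gives no correlation, SD, arm size, alpha or power for this comparison, so there is no stated figure to reproduce. Assumed: correlation ρ (within arm and gender) from 0.3 to 0.9 and SD ratio k = follow-up SD / baseline SD from 0.8 to 1.5. Intervals, power and simulations also assume 27 per arm and a two-sided 5% level.

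**Formula.** Set the baseline SD to 1. The slope of follow-up on baseline is b = ρk.

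- Planned model: Var(change) = 1 + k² − 2ρk = k²(1 − ρ²) + (1 − b)².
- Adjusted model: k²(1 − ρ²) × [1 + 1/(51 − 2)]. The bracket, 50/49 = 1.0204, is the price of estimating the slope.
- Ratio, adjusted/planned = k²(1 − ρ²)/(1 + k² − 2ρk) × 1.0204 = [1 − corr(change, baseline)²] × 1.0204.

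The ratio does not depend on the allocation between arms.

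**Equal SDs (k = 1).** The ratio becomes (1 + ρ)/2 × 1.0204. At ρ = 0.5 this is 0.75 × 1.0204 = 0.77. Equivalent n is 54/ratio. Half-widths are simulated, in baseline SD units. The last column is the power of the adjusted model for an effect that gives the planned model 80%.

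| ρ | Variance ratio | Equivalent n | 95% CI half-width, planned / adjusted | Power, adjusted |
|---|---|---|---|---|
| 0.3 | 0.66 | 81 | 0.650 / 0.529 | 93% |
| 0.5 | 0.77 | 71 | 0.548 / 0.480 | 89% |
| 0.7 | 0.87 | 62 | 0.425 / 0.396 | 85% |
| 0.9 | 0.97 | 56 | 0.246 / 0.242 | 81% |

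Break-even is where (1 + ρ)/2 = 49/50, that is ρ = 0.96.

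**Unequal SDs, ρ from 0.3 to 0.9.**

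| k | Range of ratio | Where adjustment loses (ratio above 1) |
|---|---|---|
| 0.8 | 0.51–0.65 | nowhere |
| 1.1 | 0.72–1.02 | ρ 0.83 to 0.9 |
| 1.25 | 0.80–1.02 | ρ 0.70–0.87 |
| 1.5 | 0.79–1.02 | ρ 0.55–0.76 |

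**Bounds for any k.** The ratio peaks at 1.0204 when b = 1, so the largest cost at 54 patients is 2.04% of variance. Adjustment gains whenever |corr(change, baseline)| exceeds √(1/50) = 0.14.

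**Simulation check.** With normal data, equal SDs and 20,000 runs per setting, the ratios were 0.658, 0.764, 0.863 and 0.973 at ρ = 0.3, 0.5, 0.7 and 0.9. Type I error was 0.049–0.053 for the planned model and 0.048–0.052 for the adjusted one. On a skewed raw scale (log-normal, log SD 0.5, ρ on the log scale) the ratios were 0.652, 0.734, 0.830 and 0.929, so in these settings the gain does not depend on taking logs.

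**The case against.** The planned analysis is a prespecified, accepted and valid test. It contradicts nothing in the SAP, and the choice between it and a baseline-adjusted model can be called a preference. That it is valid stands in full.

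The size of the loss in this trial is unknown, which also stands. For a marker that is very stable within a person (ρ = 0.9, equal SDs) the saving is 3% of variance. A saving of a third or more needs ρ near 0.3 with equal SDs, or a smaller SD at follow-up. At k = 1.25 or 1.5 the best saving in the range is about 20%, and in part of the range adjustment is neutral or slightly worse.

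The 2% ceiling assumes that all 54 patients enter this model. Taking 40 or 30 usable pairs for illustration, the same formula gives 1/(37 − 2) = 2.9% or 1/(27 − 2) = 4.0%. The ceiling moves but stays small.

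The outcome is secondary, and the primary outcomes that the SAP names belong to the baseline analyses, so none of those depends on this model. The SAP is written in the past tense, so the analysis may already have been done.

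These points limit the priority of the concern. They do not answer it: not knowing the slope is a reason to estimate it, since the cost of doing so is bounded and small.

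**Conclusion.** The concern holds as an optional improvement in efficiency. The model omits a baseline value that is already collected, and in doing so fixes at 1 a slope that could be estimated. With 54 patients and equal SDs, the adjusted model needs 3% to 34% less variance for ρ from 0.9 down to 0.3. It costs at most about 2%, and it loses only when the slope is close to 1. The actual gain may differ by biomarker and cannot be fixed from the SAP. The calculation assumes a linear slope and complete pairs in 54 patients. The half-widths, power and simulations also assume 27 per arm. Nothing here makes the planned test biased or invalid.

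**What to change.** Add one covariate to item 2 at follow-up. Suggested wording: *The difference in concentration (baseline minus follow-up) is analysed by a linear model with intervention arm, gender and baseline concentration, with outcome and baseline on the same scale; the arm effect is reported with a 95% confidence interval.* Keep the unadjusted change-score ANOVA as a sensitivity analysis.

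The scale is a separate decision that the item should also state. The log scale used in the baseline comparison is the natural choice, but if raw differences were intended, moving to logs changes the arm effect from a difference to a ratio. The covariate is worth adding on either scale.

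The cost is one sentence, one degree of freedom (about 2% of variance at most with 54 patients) and no new data. If results have already been seen, leave the planned ANOVA in place and report the adjusted model as an additional analysis, labelled as such.
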